There are no additional risks anticipated, specific to participating in this study. The study is not examining any experimental procedures and participation in the study is not predicted to affect the medical treatment received by enrolled subjects. The INFINITY® Total Ankle does not pose additional risks compared to other standard total ankle systems when used for the same clinical application. The risks of ankle replacement include intra-operative complications such as peri-prosthetic fracture, neurovascular damage and tendon injury. Early post-operative problems include infection, wound healing problems, deep vein thrombosis, and peri-prosthetic fracture. Late complications include infection, peri-prosthetic fracture, loosening, implant failure, ongoing pain. These risks are comparable to those in alternative implants and alternative surgical procedures.

STUDY DESIGN

Study Design

The selected design is a multi-center, non-randomized, prospective study of 500 subjects in the UK with ten investigational sites and a potential for more as needed to meet the enrollment requirements. The study subjects included are those with ankle joints damaged by severe rheumatoid arthritis, post-traumatic disease, and degenerative arthritis and implanted with the INFINITY® Total Ankle System.

Primary and Secondary Endpoints

The primary endpoint is a survivorship rate at 10 years as defined with a Kaplan Meier survivorship analysis. Secondary endpoints identify, assess and compare functional improvements or deviations collected through investigator observation and patient self-reporting, and include:

- Identification and assessment of the implant through radiographic assessment for component loosening and/or subsidence, any osteolysis and/or cyst formation early and throughout the lifetime of the implant.

- Comparison of improvements in self-reported pain and social interaction for quality of life measures from pre-op through 10 years post operatively; assessed by EQ5D5L.
- Comparison of pain and functional improvement from pre-op through 10 years in the AOS which is a visual analogue scale specifically designed as a modification of the Foot function Index.
- Comparison of the improvements in self-reported function scores from pre-op through 10 years post-operatively, assessed by MOXFQ walking/standing scores.
- Identification and reporting on the safety of the implant in terms of complications and adverse events.

[figure not shown]

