- Satisfied the Inclusion/Exclusion Criteria
- Implanted with the Device

Investigators should document subject enrollment by completing the screening and enrollment logs located within the trial master file. The Source documentation should clearly state that all inclusion and exclusion criteria have been met and the patient data release and informed consent documents have been signed and appropriately dated prior to any study related activity,

The investigative sites will be assigned three digit a site code ***, and at enrollment the subject will be assigned a sequential subject identification number corresponding to the order the subject was enrolled (i.e. the first subject enrolled at each site will be site number *** followed by subject identifier 001). The assigned codes will be used to identify the subject on all case report forms. All investigative sites will be provided protocol training of the during the site initiation visits. Investigative sites will be provided paper case report forms/booklets, which may be used as source documentation, these must signed by the individual completing the form; i.e., coordinator, patient, or investigator.

Study Duration, Subject Participation and Estimated Enrollment Period

The total study duration from , first patient, first visit, (FPFV) to last patient, last visit (LPLV) is expected to be 13 years, with a recruitment period of 36 months The investigator/investigative site must make every reasonable attempt to contact the patients to complete all scheduled post-operative visits within the visit window. In instances where the individual cannot be reached, the investigator/investigative site will document at least two attempts to contact the

patient via phone/mail and one certified letter for each time point. Due to the length of this study and the risk of lost to follow-up potential, if a subject has an inability to and, for some unforeseen reason cannot be seen on the hospital site, patient reported outcome measure case report forms may be completed remotely by post or telephone and returned to the investigative site/investigator for review and submission. If this process is applied it must be documented and reported to Wright accordingly.

Subject Withdrawal or Discontinuation

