The standard care pathway for patients undergoing Total Ankle Replacement in the UK includes the collection of Patient Reported Outcome Measures (PROMS). The study aims to use this data, wherever possible, to fulfill the secondary outcome measures of the study and avoid duplication of data collection. As there is some variance nationally regarding the questionnaires which are used for PROMS data collection, participants may be required to supplement one or more of the following questionnaires for the purposes of the research study:

Manchester-Oxford Foot Questionnaire (MOxFAQ) The MOXFAQ Patient Reported Outcome’s (PROMs) are self-administered, paper based measures consisting of 16-items and three domains: Walking/standing (7 items), Pain (5 items), and Social interaction (4 items). Response options consist of a 5-point Likert scale ranging from no limitation to maximum limitation.

EuroQol (EQ-5D5l) is a generic health survey that can be used to compare improvement across different interventions and measure changes in health-related quality of life over time.

Ankle Osteoarthritis Score (AOS) The AOS scale is a reliable, validated, visual analog based, disease specific self-administered instrument designed specifically to measure disability and pain from ankle osteoarthritis. Both Pain and Disability components are used to calculate the total score. The score is from zero to one hundred with a lower score indicating more normal function. The minimally important difference for the AOS score is not known.

Surgeon-completed Radiographic Report includes usual standard of care pre-operative radiographs will include a standing AP and lateral film of the ankle. Arthritis can be assessed by CT if available but, not required for this study.

Coronal plane deformity should be measured in degrees as the angle between a line perpendicular to the anatomical axis of the tibia and a line drawn along the top of the talar dome see (see figure) and recorded as either varus or valgus.

The Canadian Orthopaedic Foot and Ankle Society (COFAS) end-stage arthritis classification should be identified and recorded as:

Type 1: Isolated ankle arthritis

Type 2: Ankle arthritis with intra-articular varus or valgus deformity or a tight heel cord, or both

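### Telephone completion is allowed for every patient-reported form, including the AOS, a self-administered visual analogue scale for which no telephone procedure is given

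*Protocol*

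**What the plan says.** The protocol section on study duration, subject participation and enrollment period provides a remote route for subjects who "for some unforeseen reason cannot be seen on the hospital site". For them, "patient reported outcome measure case report forms may be completed remotely by post or telephone". The sentence treats all the patient-reported forms alike. A safeguard follows: "If this process is applied it must be documented and reported to Wright accordingly".

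The section on patient-reported outcome measures describes the instruments:

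- AOS: "The AOS scale is a reliable, validated, visual analog based, disease specific self-administered instrument".
- MOXFQ: "self-administered, paper based measures consisting of 16-items and three domains". On its response format: "Response options consist of a 5-point Likert scale ranging from no limitation to maximum limitation".
- EQ-5D-5L: it "is a generic health survey that can be used to compare improvement across different interventions". No mode of administration is stated.

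The list of primary and secondary endpoints includes "Comparison of pain and functional improvement from pre-op through 10 years in the AOS which is a visual analogue scale", and a parallel comparison for the MOXFQ walking/standing scores. Under Statistical Consideration, the Demographics paragraph plans pre- to post-operative comparisons of all outcome measures at each collection time point.

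**The concern.** The data-collection rule and the description of the AOS do not fit together. A subject on the telephone cannot mark a visual analogue line. Something else has to stand in for the mark, such as a spoken number, and the protocol does not say what. Sites would each have to devise their own method. The protocol calls the AOS reliable and validated as a self-administered scale, and gives no basis for extending that to a spoken version.

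The AOS result is a change from pre-op in a single non-randomized cohort. With no control arm, a shift caused by the mode of completion cannot cancel out and would read as change in the patient. The route is also selective, because it applies only to subjects who cannot be seen on site.

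For the MOXFQ the conflict is milder. Reading fixed response options aloud departs from self-completion on paper but leaves the response scale intact, so the concern is a possible mode effect and no more.

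**Working it through.** The protocol states no figure on this point, and its sample size of 500 was not calculated, so there is no number to reproduce. The check is a comparison of the texts, followed by an illustration of size.

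**Comparison by instrument**

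| Instrument | Described mode and format | Post | Telephone |
|---|---|---|---|
| AOS | self-administered, visual analogue | consistent with the description | line mark impossible by voice; no procedure given |
| MOXFQ | self-administered, paper based, 5-point Likert | consistent with the description | options can be read aloud; mode differs from the description |
| EQ-5D-5L | mode not stated | no conflict | no conflict shown |

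The same sentence thus offers one route that fits the AOS and one that does not, and leaves the choice between them open.

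**Illustration of size**

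All inputs here are assumptions except n = 500, which is the planned sample size; n = 250 is an assumed number with data at a late visit.

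- Share of forms at a visit taken by telephone: p = 0.05 to 0.30.
- Mean shift due to telephone mode on the 0 to 100 scale: d = 3 to 10 points.
- Standard deviation of the change score: 20 to 30 points.

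Bias in the mean change = p × d:

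- low end: 0.05 × 3 = 0.15 points
- middle: 0.10 × 5 = 0.5 points
- high end: 0.30 × 10 = 3.0 points

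95% confidence interval half-width = 1.96 × SD / √n:

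- n = 500: 1.96 × 20 / √500 = 1.75; 1.96 × 30 / √500 = 2.63
- n = 250: 1.96 × 20 / √250 = 2.48; 1.96 × 30 / √250 = 3.72

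If telephone use is rare, the bias is a small fraction of the sampling margin. It reaches the size of that margin only where telephone use is common and the shift is large. The protocol says that the minimally important difference for the AOS is not known, so it offers no threshold for calling such a shift important or negligible.

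**The case against.** The strongest reply is that the protocol already contains the problem. The remote route is an exception for subjects who cannot attend, post is offered alongside the telephone, and each use must be documented and reported to the sponsor. An analysis by mode may sit in a statistical analysis plan that is not shown. The forms are also to be returned to the site after remote completion, which could describe a subject marking a posted form with help over the telephone. Only secondary endpoints are involved.

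Much of this stands. It limits how often the problem can arise and makes later checking more feasible. It does not remove the gap for the AOS: the wording permits telephone completion outright, the duty to document does not expressly require the mode on each form, and no later analysis can recover a line mark that was never made. How the score is obtained is a collection rule and belongs in the protocol.

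A reader might go further and infer that telephone scores on both instruments are simply not comparable with baseline. The documents do not support that. They give no evidence on equivalence between modes, and the MOXFQ options can be read aloud. Nor do they state that baseline forms are completed in person, that the treating team would make the calls, or that remote use is confined to late visits; study length is given only as the reason for the provision. A reader might also conclude that telephone values should be left out of the main comparison. With an assumed 10% to 30% of forms, that would drop 0.10 × 500 = 50 to 0.30 × 500 = 150 subjects at a visit before attrition. These are the subjects who cannot attend, whose missingness is plausibly informative. The exclusion could introduce a selection bias in place of a mode effect of unknown size.

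**Conclusion.** The point holds for the AOS as an inconsistency within the protocol: telephone completion is permitted for a scale that cannot be completed by voice as described, and no procedure is given. For the MOXFQ it holds only as a possible mode effect. No conflict is shown for the EQ-5D-5L.

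The consequence is a risk of bias in uncontrolled change-from-pre-op comparisons that are secondary endpoints. The primary endpoint, Kaplan-Meier survivorship at 10 years, is unaffected. The size cannot be determined from the documents; the range of 0.15 to 3.0 points rests wholly on assumed telephone shares and shifts. This is a worthwhile, inexpensive correction to a collection rule, and it does not threaten the study's main result.

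**What to change.** Amend the remote-completion sentence in the section on study duration and participation so that the AOS, and preferably the MOXFQ, is completed remotely only by the subject on the posted paper form. Keep the telephone for reminders and for checking missing items.

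Build on the existing duty to document remote use by adding one field to each patient-reported form for mode of completion: site, post or telephone. Mode that is not captured at the time may be hard to reconstruct in a study expected to last 13 years.

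If any telephone values are collected, keep them in the main comparison and examine their influence in a sensitivity analysis by mode.

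The cost is a short protocol amendment, one field per form, and postage. The downside is that a few AOS forms which might have been taken by telephone may be missing.

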Planned visits and Follow-Up Time Points

Subjects will be seen prospectively at the following intervals Pre-Op, Operative, 6 months, 1, 2, 5, 7, and 10 years. If there are special circumstances where the subjects require a visit outside the windows of the established visits, the investigator may seek approval from Wright Medical for an acceptance of an “unscheduled visit” and it will be determined if the data will be included and analyzed.

SITE/SUBJECT SELECTION

Clinical Research Sites will be identified to participate in the study based on current experience, and training in the use of the INFINITY® Total Ankle System and according to ICH GCP guidelines and ISO 14155: 2011 which states; qualified by education, training and experience to perform his or her respective task(s). It is the expectation the surgeon will adhere to and follow the INFINITY® Surgical Technique and have knowledge of the contraindications as provided in the Instructions for Use (IFU). (See Appendix A).

Study Design Summary

Informed Consent

Subjects will be recruited based on interest in participating in the study. All subjects will be consented by an appropriately trained clinician or research nurse using the REC approved information sheet and consent form in order to participate in the study and prior to any data collection, or any study procedure. The study clinician or research nurse will assess whether the patient can give informed consent or not during the consent process, in compliance with the 2005 Mental Capacity Act. The potential participant must be allowed ample time to review the informed consent and should be allowed to take the time to read, review, ask questions, and receive answers as well as being fully informed of all aspects of the study before a decision is made to participate. The source documentation will include a statement of the consent process and include details of the person taking consent for study participation.

Screening

Subjects with interest in participating in the study, after signing the informed consent document, will then be invited to participate if they meet the Inclusion Criteria.

Point of Enrollment

Subjects will be considered enrolled in the study when they have:

- Been informed of all aspects of the study and have signed or have their verbal consent witnessed on the Informed Consent document
- Acknowledged the appropriate patient data release information (included in the Informed Consent document)

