Subjects maintain the right to discontinue their participation in the study at any point without penalty or loss of benefit to which the subject is otherwise entitled per ICH E6 4.8.10(m) guidelines. Although, a subject is not obliged to give his or her reason(s) for withdrawing prematurely from this study, the investigator should make a reasonable effort to ascertain the reason(s), while fully respecting the subject's rights per ICH E6 4.3.4 guidelines.

Device Failure

Subjects will be considered a treatment failure, and will be withdrawn from the study if any sections of the device (tibial or talar metal components) have been removed at any time during their participation. This should be reported onto the adverse event form. In addition, any surgical intervention during study participation that relates to their total ankle replacement will be reported on the surgical intervention case report form.

Procedures and Case Report Forms

Subject medical history and demographic information will be collected and recorded onto the demographic case report form. The following information will be collected on these forms:

- Date of birth
- Gender
- Height
- Weight
- BMI calculation
- Smoking status
- Status of other joints that affect ambulation (i.e., knee replacement, contralateral arthritis and/or ankle replacement)
- Concomitant health conditions (diabetes and other medical conditions, etc.)

Operative Procedure Information

The information related to the subject's operation will be collected and recorded according to the Operative Information Case Report Forms. The following operative information related to the primary TAR procedure will be documented on these forms:

- Primary diagnosis
- Any previous surgery to index joint
- Date of operation
- Site location
- Surgical approach
 - Instrumentation type (standard) or (additional approved INFINITY® instrumentation)

- List concomitant operative procedures such as tendon/deltoid lengthening or other reconstructive process required to make final implantation correct
- Cement use
- Intraoperative complications (to be collected on the Adverse Event Case Report Form)
- Product description and eight-digit product code for all components implanted

Patient Reported Outcome Measures (PROMS)

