- intra-articular ankle varus or valgus alignment was defined as the angle of the proximal talar surface (talar tilt) to the lateral border of the tibia in the distal diaphysis and metaphyseal region more than 10 degrees on the AP weightbearing ankle views
- Type 3: Ankle arthritis with hindfoot deformity, tibial malunion, midfoot abductus or adductus, supinated midfoot, plantar flexed first ray, etc.
- hindfoot deformity defined as the angle between the lateral border of the calcaneus and the long axis of the tibia on the AP view of the ankle (varus more than 5 degrees, valgus more than 10 degrees)
- Tibial deformity defined as an angulation between the lateral border of the tibia more than 10 degrees on the AP view of the ankle **

Type 4: Types 1, 2, and 3 plus subtalar, calcaneocuboid, or talonavicular arthritis **

The post-operative radiographic evaluations will be to assess, record, and report migration, loosening, subsidence of the device, any osteolysis and cyst formation.

Notes:

* Greater than 10 degrees (defined as the angle between a line perpendicular to the anatomical axis of the tibia and a line drawn along the top of the talar dome (see figure) and recorded as either varus or valgus

** If the patient has required staged surgical deformity as part of the management of the ankle arthritis (within 18 months of TAR), this should be considered a type 3. However, if the patient has undergone historic corrective surgery then the current foot position should be used for the purpose of COFAS grading (ie, if fully corrected and then can be Grade I).

*** this would include patients with prior arthrodesis of the subtalar, calcaneocuboid, or talonavicular joints.

STATISTICAL CONSIDERATION

Sample Size

The total sample size is 500 subjects. The sample size was not calculated using statistical methods. A non-parametric statistical analysis for survivorship using the Kaplan-Meier will be applied to determine the implant survivorship.

This total sample size is based on historical knowledge and a precedent being set for the UK by “The Orthopaedic Data Evaluation Panel” (ODEP) ratings for arthroplasty implants. Mechanical survivorship for total hip and knee replacement is currently thought to be approximately 10 years. This benchmark for long-term data collection is not only

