All information will be collected according to the protocol and defined case report forms. Investigator subject records (e.g. medical records, imaging reports, surgical notes or, paper case report form booklets) will be considered source documents for the study. This information will be entered by the site through a website provided by Wright Medical. Data will be received by Wright Medical through the electronic data capture system. The vendor for the electronic data capture system maintains a certification for safe harbor regulations in the EU/EEA. The Investigator must allow Wright Medical or its representative's access to the subject files. This access includes inspection of records.

In order to facilitate potential site monitoring visits, the investigator is required to keep records, including the identity of all participating subjects, all original signed Informed Consent Documents, and source documents. These records must be retained by the Investigating site according to local regulations as specified in the Clinical Trial Agreement.

If the Investigator relocates, retires, or for any reason withdraws from the study, Wright Medical should be notified ahead of time. The study records must then be transferred to an acceptable designee (another investigator, institution, or Wright Medical). The investigator must obtain Wright Medical's written permission before disposing of any records.

Participant Confidentiality

The study team will ensure that the participants' anonymity is maintained. The participants will be identified only by study number on the electronic CRF. All documents will be stored securely and only accessible by study staff and authorised personnel. The study will comply with the Data Protection Act which requires data to be anonymised as soon as it is practical to do so. To ensure confidentiality, none of the data stored or transferred electronically will contain personal identifiers.

Monitoring Plan

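### No step establishes implant status for subjects who withdraw or cannot be reached, although 10-year implant survivorship is the primary endpoint and site records are already source documents

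*Protocol*

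**What the plan says.** Under Primary and Secondary Endpoints: "The primary endpoint is a survivorship rate at 10 years as defined with a Kaplan Meier survivorship analysis". Visits are widely spaced: "Subjects will be seen prospectively at the following intervals Pre-Op, Operative, 6 months, 1, 2, 5, 7, and 10 years".

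Four rules in the protocol bear on subjects who leave or stop attending:

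- **Withdrawal** (Subject Withdrawal or Discontinuation): "Subjects maintain the right to discontinue their participation in the study at any point without penalty". The investigator should make a reasonable effort to learn why. Nothing is said about implant status at exit or afterwards.
- **Unreachable** (Study Duration, Subject Participation and Estimated Enrollment Period): the site documents at least two attempts to reach the "patient via phone/mail and one certified letter for each time point". No further step follows.
- **Unable to attend** (same section): questionnaires may be completed by post or telephone. These serve the secondary outcomes.
- **Failure definition** (Device Failure): removal of a tibial or talar metal component counts if it happens while the subject is participating. Surgical interventions on the replacement are reportable over the same period.

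Under Data Management: "Investigator subject records (e.g. medical records, imaging reports, surgical notes or, paper case report form booklets) will be considered source documents". A footnote to the Schedule of Events adds that standard-care X-rays are collected every year, and another that surgical interventions are watched for during participation.

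**The concern.** A Kaplan-Meier estimate of implant survival needs to know, for each subject, whether the implant is in place and up to what date. The protocol provides a fallback for the questionnaires but none for the primary endpoint, although it names loss to follow-up as a risk of so long a study. Records that could often settle the question already sit at the site.

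If subjects with a painful or failing ankle are more likely to stop attending or to seek care elsewhere, their later failures go unseen and survivorship is overstated. An analysis plan can choose a censoring rule or a sensitivity analysis. It cannot supply implant-status data that sites were not told to collect or that subjects were not asked to allow. That makes this a matter for the protocol.

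**Working it through.** **The plan's own figures.** "The total sample size is 500 subjects", and "The sample size was not calculated using statistical methods", so there is no event rate, loss rate or precision target to reproduce. The study duration "is expected to be 13 years, with a recruitment period of 36 months"; 36 months plus 10 years is 13 years, which agrees.

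**Assumptions (none is in the protocol).**
- Failure hazard while followed: λ = 0.008 per year.
- Cumulative loss by 10 years, from withdrawal or lost contact: 20%, 30% or 40%, at constant rate g = −ln(1 − loss)/10.
- Hazard after loss: HR × λ, with HR from 0.5 to 3.
- Lost subjects are censored at last contact. This is a working assumption, since the protocol gives no censoring rule.

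**Formulae.** The Kaplan-Meier estimate converges to exp(−10λ) = exp(−0.08) = 0.923. True survivorship, with a = λ + g − HR·λ, is

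S(10) = exp(−10(λ+g)) + g·exp(−10·HR·λ)·(1 − exp(−10a))/a.

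**Worked case, 30% loss and HR 2.** g = 0.03567, λ + g = 0.04367 and a = 0.02767. The first term is exp(−0.4367) = 0.646. The second is 0.03567 × 0.852 × (1 − 0.758)/0.02767 = 0.266. The sum is 0.912, so the overstatement is 0.923 − 0.912 = 1.1 points.

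**Error of the reported rate, in percentage points (positive = overstated):**

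| Loss by 10 years | HR 0.5 | HR 1 | HR 1.5 | HR 2 | HR 3 |
|---|---|---|---|---|---|
| 20% | −0.4 | 0 | 0.4 | 0.7 | 1.5 |
| 30% | −0.6 | 0 | 0.6 | 1.1 | 2.2 |
| 40% | −0.8 | 0 | 0.8 | 1.6 | 3.0 |

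For HR 1.5 to 3 this means about 6 to 23 failures after loss per 500 subjects.

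**Sensitivity to the failure rate, loss 10 to 40%.** With Kaplan-Meier survivorship of 95%, the overstatement is 0.2 to 1.0 points at HR 2 and 0.5 to 2.0 at HR 3. With 90% it is 0.5 to 2.0 and 0.9 to 3.8. With 85% it is 0.7 to 2.8 and 1.3 to 5.4.

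**Scale.** The 95% half-width with 500 subjects and no loss is 1.96 × √(0.923 × 0.077/500) = 2.3 points. The mid case is about half of that; the upper end exceeds it.

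**How a records check must be analysed.** Suppose failures found in the records are counted whenever they occur, while subjects with no failure on record stay censored at last contact. Simulation at 30% loss then gives survivorship 1.4 points too low at HR 1 and 1.6 too low at HR 2 if every failure is found, and 1.1 too low at HR 2 if 80% are found. If every failure is found and each checked subject is followed to the same check date whatever the result, the bias disappears.

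**The case against.** The strongest counter-case has five parts.

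- **Unreachable subjects have not left.** They are tried again at each time point, interventions are watched for throughout participation, and hospital records are source documents. A same-site revision is therefore already reportable. This stands: a reader might infer that these subjects vanish from the primary endpoint, and the protocol does not say so. What is missing is a step to find the event.
- **No censoring rule is stated.** A reader might infer that the protocol censors everyone at last contact. It does not say this, and such a rule commonly sits in the analysis plan. This stands.
- **The right to withdraw is not an error.** Agreed. The gap is in what the protocol asks the site to do once the right is used. The consent document and case report forms are not at hand and may already allow later use of records. Even so, the protocol text would not count a removal found that way, because its failure definition ends with participation.
- **The direction of bias is a hypothesis.** Subjects may leave because they are frail, have moved or are doing well. At HR 0.5 the estimate is 0.4 to 0.8 points too low. A reader might infer that the result must favour the device; the documents do not support that.
- **A records check can itself bias the result.** This stands for one-sided counting, as the simulation shows, and it shapes the fix. Surgery at another hospital would also be missed.

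**Conclusion.** The gap is real and worth closing, though narrower than a claim that the primary endpoint is biased. For withdrawn subjects, no determination of implant status is required and later removals lie outside the failure definition. For unreachable subjects, a revision is reportable but no procedure is set to find it.

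The consequence is conditional. Under the assumed rates, survivorship is overstated by 0.4 to 3.0 points if leavers fail 1.5 to 3 times as often as stayers. It is unbiased but less precise if the hazards are equal, and understated if leavers fail less often. The protocol gives no rates from which to choose among these cases, and without implant-status data the study could not tell them apart afterwards.

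**What to change.** 1. **Subject Withdrawal or Discontinuation, and Device Failure.** At withdrawal, record implant status and its date, and whether the subject is stopping visits only or all use of data. Where consent allows, continue to take implant status from routine hospital records to 10 years, and let removals found this way count as failures.
2. **Study Duration, Subject Participation and Estimated Enrollment Period.** After failed contact at a time point, the site checks its own records. It enters the status (in place, removed with date, or died with date) and the date to which the records support it.
3. **Treat failures and non-failures alike.** Check all such subjects at the same fixed time points. In the analysis, follow each checked subject to the same check date whether or not a removal is found; alternatively, count record-found failures only up to the date to which non-failures are also followed. Do not count late failures while censoring non-failures at last contact. Report the estimate censored at last contact as a sensitivity analysis.

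The cost is a short record check by existing site staff, a case report form item and possibly a line in the patient information. Revisions at other hospitals may still be missed, so some overstatement can remain.
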